## 8.1.3. Physical function testing

• Participants will complete a 6-minute walk test during scheduled remote assessments at 21 days, 3 months, 6 months, 12 months and 24 months. Participants can choose a convenient location to complete this task (e.g. local park or street), but it should be the same place across all measured time points. The test will be synchronised with the Garmin device and recorded data completed within the app.

#### Outcome measures obtained from test are:

- Distance travelled
- Perceived exertion (CR10 scale: 1-10)
- Perceived fatigue (CR10 scale: 1-10).

## 8.1.4. Patient Reported Outcome Measures (PROMs)

The measures listed in 7.6.1 are completed as an app-based questionnaire, including global outcome, mental health, headache, vision, vestibular and sleep questionnaires.

## 8.1.5. Cognition

All participants will complete a familiarisation session with the full battery of tests with remote support before any formal testing. This will not be recorded as outcome data, but instead allows participants to become familiar with the task instructions and requirements.

Tests will be completed using a computerised cognitive battery on the Cognitron platform (https://www.cognitron.co.uk/). This includes a core set of tests optimised for assessing multiple dimensions of cognition that are likely to be affected in mild to moderate TBI patients, alongside several additional tasks capturing more subtle executive and reasoning problems (marked with \*).

• Immediate & delayed recall: participants are presented with a sequence of objects to memorise at the start of the battery. They are then presented with an array of objects and must indicate which they have seen before, including foils that are semantically similar. Recognition memory is repeated at the end of the battery, capturing delayed recall.

NB. Alongside assessing memory, this task allows us to flag poor effort (as occurs with

functional cognitive disorder), as most participants will score quite high, though not at ceiling.

- **2D manipulations:** participants are presented with a 6x6 grid containing 6 coloured squares, and 4 possible responses that include the same pattern rotated in space. The task continues for 3 minutes, and the score reflects the number of correct responses.
- **Picture completion:** participants are presented with pictures of scenes on a 5x5 grid with a number of empty cells for them to complete by selecting the right cell from an array that includes rotated cells and distractors. There are 12 trials and scores reflect the total number of errors.
- Simple Reaction Time: participants see a target in an unpredictable location on the screen at an unpredictable offset and have to respond as quickly as possible by clicking in the centre of it. The task runs until 60 responses are submitted. Scores reflect the mean reaction time and distance from target, as well as motor accuracy and delay as a function of intertrial spatial distance.
- **Choice Reaction Time:** participants see an arrow in the centre of the screen pointing to the left or the right and have to respond as quickly as possible by clicking on the side of the screen that the arrow is pointing. The task runs until 60 responses are submitted. Scores reflect the mean reaction time for correct responses.
- Switching Stroop: The Switching Stroop task measures aspects of attentional control in a brief efficient format. These include (a) processing speed, (b) costs associated with attention switching and (c) costs associated with interference between incongruent information. The task runs for 2 minutes, during which time participants make binary stimulus discrimination decisions as quickly as they can. We have found this to be amongst the most sensitive tasks in a variety of clinical populations, for example, Multiple Sclerosis, Parkinson's disease and REM Sleep Behaviour Disorder patients all find this to be a particularly challenging task. it also is sensitive to subtle deficits in early stage and prodromal populations, making it a good candidate task for measuring subtle attentional control deficits in people who have suffered mild-moderate traumatic brain injuries.
- **Card pairs:** this task includes a set of 12 face-up cards containing paired figures for the participants to memorise. After 7 seconds, the cards turn down and participants have to identify each pair. There are 5 trials and the score reflects the percentage of correct responses.
- **Tower of London\*:** participants are presented with two sets of 3 pegs that have 3 coloured blocks on each. They have to calculate the fewest number of moves required for the balls in the first set to be moved into the position displayed by the second, moving only one at a time. There are 10 trials and the score reflects the correct number of responses.
- **Trail Making:** This task includes two blocks. In the first, they see numbers 1-26 on the screen and are asked to click on them in numerical order as fast as they can. In the second block, they see numbers 1-13 and letters A-M and they are asked to alternate between them in numerical and alphabetical order respectively (e.g., 1, A, 2, B, etc.). Scores represent reaction times for each task, as well as a measure of the additional load in the second block as compared to the first one.
- **Paired Associates:** working memory task where participants are presented with a sequence of objects in spatial locations that they must remember. They are then probed with the

objects and must indicate the location that they were in. The number of object-location paired associates increases with each correct response until participants give 3 consecutive incorrect responses. The score reflects the maximum number of paired associates they can memorise.

- Verbal analogies\*: verbal reasoning task where participants are presented with two statements regarding the relationships between pairs of words and must decide if the nature of the relationships are the same. The score reflects the number of correctly solved problems in two minutes.
- Word definitions: unusual words are displayed on the screen. The participant must select from amongst four definitions of the words based in part on their experience of the words, but also their knowledge of the relationship between the form and meaning of words. The score reflects the number of correctly identified word definitions.
- **Continuous attention task\*:** A series of digits on noisy backgrounds appear briefly on the screen. The outcome measure is detection rate, and this is broken down by time segment, capturing loss of sustained attention to the continuous monitoring of the task. Every 40 seconds, a visual analogue scale captures information about fatigue and motivation, enabling changes in these to be analysed as participants progress through the task.

Interspersed with the tests are brief questions probing participants' perceptions on their performance. This allows metacognitive awareness to be assessed. Metacognitive awareness is relevant to TBI patients, a subset of whom lack insight into their impairments.

## 8.1.6. Cognitive mini-battery assessment

In addition, we will deploy a very brief (~5 minutes) battery to be used weekly during the first 2 weeks following the 21-day assessments, as well as in 1 month periods at 6, 12 and 24 months, alongside sleep recordings with a wearable device (actigraph) and a daily sleep diary. This minibattery will consist of the immediate & delayed recall test, simple reaction time test, and continuous attention task (outlined in 8.1.5 above, tasks underlined).

## 8.2. Clinical procedures

## 8.2.1. Clinical history

Prior to a first clinical assessment visit, the following will be recorded during a structured interview which may take place remotely:

- **Demographic details:** Age, sex at birth, ethnicity, race, sexuality, socioeconomic deprivation (assessed by postcode), education (highest level reached), functioning (highest ever and last 12 months), civilian or military, litigation activities.
- **Physical Health:** Past medical history, history of TBI (including traumatic/non-traumatic, blast scoring, severity (GCS, VA/DoD), number of days hospitalised, post-traumatic amnesia), menstrual history (if appropriate).
- **Mental Health:** Past psychiatric history, Medication history (current and past), Trauma type (assault vs. non-assault), PCL-5, MINI Diagnostic Interview for DSM-5, Social and Occupational Functioning Assessment Scale (SOFAS), Alcohol/substance use
- **Headache:** Headache history obtained by structured clinical interview. Headache phenotype (according to criteria from the International Headache Society) will be assessed.
- Glasgow Outcome Scale Extended (GOS-E): A questionnaire which categorises the

outcomes of patients after TBI.

#### 8.2.2. Clinical examination

The following will be recorded during clinical examination at the clinical assessment visit:

- Height: will be measured to the nearest 0.1 cm with a rigid stadiometer.
- **Body mass**: will be measured in light indoor clothing to the nearest 0.1 kg.
- **Brachial blood pressure:** will be measured as recommended by the British Hypertension Society (http://www.bhsoc.org/how\_to\_measure\_blood\_pressure.stm) three times in the sitting position using standardised blood pressure monitors. The average of the second and third blood pressure readings will be recorded.

## 8.2.3. Biofluid sampling

Samples will be collected between 0900-1000 hours wherever possible. Participants will give samples consisting of:

- **Blood samples:** collected via peripheral vein as per normal clinical practice. Approximately 30ml total will be collected: 4ml in an EDTA tube for plasma (only at Visit 1) and 3.5ml for serum for the local NHS pathology lab to analyse as per local practice, and 10ml in EDTA aprotinin tubes for plasma and 12ml for serum to be processed before being transferred to and stored for future analysis at UOB.
- Saliva samples: as per normal clinical practice.
- **Hair samples:** as per normal clinical practice from crown of head if possible (taken only at the 21 day visit ("Visit 3").
- **Tears samples:** Basal (unstimulated) tear fluid samples (approximately 5-10 microlitres per eye) will be collected by capillary flow from the inferior lateral meniscus of each eye using disposable microcapillary tubes. Tear samples will be stored locally until required for analysis.

## 8.2.3.1. Laboratory procedures

Full details of sample processing will be described in a separate study laboratory manual. It will be the responsibility of the local PI to maintain a sample log, recording samples collected, stored, and sent. All samples will be collected and then either stored and analysed locally where necessary or processed and then sent to the University of Birmingham (UoB) Human Biomaterials Resource Centre (HBRC) biobank for storage and analysis.

## 8.3. Visual assessments

Visual assessment acquisition will be specified in the visual assessment study manual.

To assess retinal and optic nerve structure:

• **OCT:** Heidelberg OCT will be performed including posterior pole, disc volume and RNFL scans and OCTA will be performed including optic nerve head and macula (20°x20°) scans.

To assess visual function:

- **Visual acuity:** uniocular best corrected log of the minimum angle of resolution (logMar), will be recorded using a chart or Acuity Plus.
- **Visual field assessment:** automated perimetry (Humphrey 24-2 SITA fast central threshold) will be performed to measure visual field sensitivity.

- **Colour vision:** Colour Assessment and Diagnosis.
- Visual reaction and processing time: Eye Movements and Intrinsic Latency.
- Contrast sensitivity: Pelli Robson chart or Acuity Plus.
- Pupillometry: NeuroOptics DP2000.
- Accommodation: Autorefraction

#### 8.4. Vestibular assessments

Vestibular assessment acquisition will be specified in the vestibular assessment SOPs.

- **Dix-Hallpike manoeuvre (DHPM)** for BPPV. Trained individual carries out DHPM and assesses for presence of nystagmus as well as evoked feelings of vertigo. If BPPV is present carry out Epley manoeuvre.
- Assessment of eye movements: Eye-tracking goggles (VNG) will be worn to record eye movements whilst the participant carries out the test battery set up within the protocol. The protocol assesses various vestibular evoked eye movement responses such as: optokinetic nystagmus, Saccades, anti-saccades, and smooth pursuit.
- **Posturography +EEG/EMG (sway test):** Measurements of balance will be recorded whilst the participant is on a platform with varying conditions (Feet apart, eyes open; feet apart eyes closed; feet together, eyes open; feet together eyes closed).
- Assessment of walking: Romberg test with eyes closed over 20 seconds, tandem walking errors over 10 steps, tandem standing with eyes open over 20 seconds and eyes closed over 20 seconds.
- **vHIT**: To assess function of all 6 semicircular canals within the vestibular system.
- **Tympanometry**: Pressure inside the inner ear will be assessed to determine if any abnormalities are present. Acoustic reflex will be assessed.
- **PTA**: A full PTA will be carried out to identify hearing function.
- Vestibular-evoked myogenic potentials and auditory-evoked potentials: To assess otolithic pathways. Visual vertical assessment (computer-based) as additional assessment of otolithic function.
- Electrical Vestibular Stimulation (EVS): To assess if any delay in vestibular ocular responses are present.

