# List of primary biomarkers by workstream

Workstream	Assessment	Primary biomarker
Global		
	Return to work/duty/play	Yes/No
	Mayo-Portland adaptability inventory	Score
Headache		
	Headache diary	Monthly headache days
Mental health		
	PCL-5 (Post-Traumatic Stress Disorder checklist for DSM-5)	PTSD (Post-traumatic stress disorder) Yes/No
Vestibular		
	vHIT (video Head Impulse Test)	Gain value of all 6 semicircular canals
Cognition		
	Cognitive battery	Corrected Global Composite Score
Visual		
	OCT (Optical coherence tomography)	RNFL thickness (Retinal nerve fibre layer thickness)
Imaging		
	MEG (Magnetoencephalography)	Delta/theta waves
	Structural MRI (Magnetic resonance imaging)	FA (fractional anisotropy) / MD (mean diffusivity)
	Functional MRI	Dynamic connectivity (mean dwell time)
	Physiology fMRI	Cerebrovascular reactivity (CVR)
Fluid / hormone		
	Blood	Glial Fibrillary Acidic Protein
	Blood	Cortisol
Cerebral physiology		
	Doppler	Cerebrovascular reactivity (CVR)
	fNIRS (Functional near-infrared spectroscopy)	Neurovascular coupling (relative change in oxy- and deoxyhaemoglobin)
	TMS (Transcranial magnetic stimulation)	Cortical silent period
	EEG (Electroencephalogram)	Delta/theta waves
	Physical function	6-Minute Walk Test
	Exercise capacity	Maximal voluntary contraction / muscular endurance )

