## All visits should be completed within the time window given here. All time points given are postinjury.

*Note*: Visit 5 is an additional visit of exploratory imaging and will be discontinued after 50 mTBI patients have completed both it and visit 10.

Visit 12 is an additional visit and will be discontinued after 100 mTBI patients have completed it.

For the candidate biological variability study (Figure 1):

- 20 mTBI patients will repeat visit 3 (clinical) on an extra three occasions within 12 days (4 clinical visits in total).
- 20 further mTBI patients will repeat visit 4 (imaging) on an extra three occasions within 12 days (4 imaging visits in total).

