## 7.6.2. Visit 3 - Clinical assessment day

*Note:* 20 mTBI patients and 20 healthy controls will repeat these assessments on three additional occasions in 12 days, as part of the variability nested study (only saliva/blood/tears biomarker samples, visual assessments, vestibular, cerebral physiology repeated). Participants will be asked to avoid consuming caffeine before and during these assessments. Participants will also be asked to avoid vigorous exercist and the consumption of alcohol 24 hours prior to the visit. Decaffeinated drinks will be provided at the hospital.

Participants will attend a clinical research facility where the following data will be collected.

\* these elements of the clinical assessment may be done remotely before the visit

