#### Vestibular assessments:

- Vestibular history\*
- Dix-Hallpike manoeuvre to assess BPPV
- Assessment of eye movements (VNG)
- Posturography
- Assessment of walking
- Vestibular reflex (vHIT) Tympanometry
- Pure tone audiogram (PTA)
- Vestibular-evoke myogenic potentials and auditory-evoked potentials
- Electrical Vestibular Stimulation (EVS)

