# **11. DATA HANDLING AND RECORD KEEPING**

## 11.1. Source data

Source data is defined as all information in original records and certified copies of original records of clinical findings, observations, or other activities in a clinical study necessary for the reconstruction and evaluation of the study. To allow for the accurate reconstruction of the study and clinical management of participants, source data will be accessible and maintained.

Some data variables may be entered directly onto the eCRF, these are clearly identified and detailed in **Table 5**: Source data in mTBI-Predict.

Source data is kept as part of the participants' medical notes generated and maintained at site. In addition, for this study, brain imaging (MRI and MEG) is performed; the source data will be the original output files directly uploaded to the UoB Research Data Store. Similarly, vestibular and physiology workstreams will include the collection of continuously measured electronic data which will be uploaded and stored within the UoB Research Data Store.

Data	Source
Participant Reported Outcomes	The original participant eCRF completed via the app and imported directly into the study database is the source.
Lab results	The original lab report (which may be electronic) is the source and will be kept and maintained in line with normal local practice. For tests performed at NHS labs, information will be transcribed onto the eCRF.
Imaging	The source is the original pseudonymised electronic imaging output file uploaded to the Study Office (via UoB Research Data Store). When data is then interpreted, the eCRF onto which it is transcribed becomes the source.
Mental Health	The MINI Assessment for the DSM-5.
Cerebral Physiology Data	The source is continuously collected raw data files acquired through either Labchart, Spike or native software, uploaded to the Study Office (via UoB Research Data Store). These data include outputs from TCD, , NIRS, EEG, TMS (EMG), Processed and analysed data will be imported into the eCRF in CSV format.
Vestibular Data	
 
Scores will be collected during the following tests:
 
Dix-Hallpike, Walking assessments.
 
Continuous data will be collected and uploaded from the following tests:
 
Posturography, VNG, vHIT, Tympanometry, PTA, VEMPs, EVS.
 

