# **14. STATISTICAL CONSIDERATIONS**

### 14.1. Biological variability studies

We will recruit 20 healthy controls and 20 mTBI patients to both the clinical and imaging

assessments days of the study at the 21-day visit (in total 40 healthy controls and 40 mTBI patients). Each participant will then undergo an additional three (or five in the case of imaging for healthy controls) measurements of each biomarker over a 12-day (or 19-day for imaging) period. For some biomarkers (e.g. fluid biomarkers) variability will be assessed by analysis of samples in quadruplicate.

For each of the biomarkers under investigation (see Appendix 1), we will estimate the variability at the within-individual and the between-individual level. For example, for the 20 healthy controls or mTBI patients, if the analytical standard deviation was 0.5, the within-individual standard deviation was 1.0 and the between-individual standard deviation was 2.3, approximate confidence intervals for these estimates would be (0.45, 0.56), (0.79, 1.19) and (1.56, 3.05), respectively. These values would yield an ICC of approximately 80% with a 95% confidence interval ranging from 65% to 89%. All confidence interval estimates have been calculated using simulation. We will not reassess at the 3-month time point as we will assume that variability at 21 days will be greater than at 3 months.

We will use multilevel models to estimate the variability at each level, with log transformation of the biomarker outcomes if necessary, for the healthy and mTBI patients combined and separately. We will express the results from this stage of the study as standard deviations, coefficients of variation, ICCs, reference change values and other relevant variability estimates along with 95% confidence intervals as appropriate. Within the imaging variability study, we will also investigate the variability between centres (University of Birmingham, Aston University, and University of Nottingham) using the same method. For this purpose, the 20 healthy participants will have three additional measurements at the centre used at their 21-day visit, alongside additional imaging visits at the two alternative imaging centres (five total variability visits).

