## **23. APPENDICES**

# 23.1. Appendix 1: Complete list of biomarkers

General	R-PSQ	Score
	MPAI	Score
	QoLiBri	Score
	Pain Catastrophizing Scale	Score
	PVAC	Score
	Perceived Injustice Questionnaire	Score
	Locus of Control Questionnaire	Score
	6-minute walk test	Distance
	6-minute walk test	Perceived Exertion
	6-minute walk test	Perceived fatigue
	GOS-E	Score
Headache		
	Headache phenotype	ICHD phenotype
	Headache diary	Headache presence yes/no
	Headache diary	Monthly headache incidence
	Headache diary	Incidence of moderate to severe intensity
		headache
	Headache diary	Headache pain intensity 0-timepoint
	Headache diary	Headache pain intensity over time
	Headache diary	Headache days per month from 0-
		timepoint
	HIT-6 (Headache impact test – 6)	Score
	STAI (Trait anxiety score)	Score
	Photosensitivity assessment	Score
	questionnaire	
	Hyperacusis questionnaire	Score
	12 item allodynia	Score
Mental health		
	SOFAS	Score
	PCL-5	PTSD Yes/No
	MINI DSM-5	PTSD Yes/No
	MINI DSM-5 (PTSD supplement)	PTSD Yes/No
	PHQ-9	Score
	GAD-7	Score
	SBQ-R	Score
	AUDIT	Score
Vestibular		
	Dix-Hallpike Manoeuvre	BPPV
	Balance Vigilance Questionnaire	Score
	VVQ	Score
	DHI	Score
	ABC	Score
	BSQ	Score
	EVS	Continuous Data
	Posturography	Magnitude of sway (milimetres))
	Eye movements	Smooth pursuit

	Eye movements	Saccades
	Eye movements	Anti-saccades
	Acoustic reflex	Amplitude (volts), Latency (millisecond)
	РТА	dB
	Vestibular-evoked myogenic potentials	Amplitude (volts), Latency (millisecond)
	vHIT	Continuous data (Gain and catchup saccades)
Cognition		
	PSQI	Score
	rMEQ	Score
	ESS	Score
	FSS	Score
	ISI	Score
	BQ	Score
	Cognitive battery	Correct Global composite score
	Actigraphy	Daily level of activity
	Cognitive battery	Immediate & delayed recall
	Cognitive battery	2D manipulations
	Cognitive battery	Picture completion
	Cognitive battery	Simple Reaction Time
	Cognitive battery	Choice Reaction Time
	Cognitive battery	Card pairs
	Cognitive battery	Tower of London
	Cognitive battery	Trail Making
	Cognitive battery	Paired Associates
	Cognitive battery	Verbal analogies
	Cognitive battery	Word definitions
	Cognitive battery	Continuous attention task
Visual	,	
	ОСТ	Macular ganglion cell layer thickness (global)
	ОСТ	Macular ganglion cell layer thickness (sectoral)
	ОСТ	Optic disc volume
	ОСТ	RNFL thickness (global)
	ОСТ	RNFL thickness (sectoral)
	ΟCTA	Optic nerve head peripapillary flow indices (e.g superficial vascular plexus, skeletal fractal dimension)

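### The Epley manoeuvre that section 8.4 requires after a positive Dix-Hallpike would be counted as random within-person fluctuation of that test in the mTBI variability cohort

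*Protocol*

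**What the plan says.** The point depends on several sections of the Protocol read together.

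- **Treatment rule.** Section 8.4, on Dix-Hallpike: "If BPPV is present carry out Epley manoeuvre". No cohort or visit is exempted.
- **Place in the battery.** The visit 3 vestibular list in 7.6.2 includes "Dix-Hallpike manoeuvre to assess BPPV".
- **Repetition.** Section 7.1: "20 mTBI patients will repeat visit 3 (clinical) on an extra three occasions within 12 days (4 clinical visits in total"). The note in 7.6.2 says what is repeated: "only saliva/blood/tears biomarker samples, visual assessments, vestibular, cerebral physiology repeated".
- **Data capture.** The source data table in 11.1 names the vestibular tests that yield scores: "Dix-Hallpike, Walking assessments".
- **Biomarker status.** Appendix 1 (23.1) lists "Dix-Hallpike Manoeuvre", with BPPV as the biomarker. The primary vestibular biomarker is a different one, from vHIT: "Gain value of all 6 semicircular canals".
- **Analysis.** Section 14.1: "For each of the biomarkers under investigation (see Appendix 1), we will estimate the variability at the within-individual and the between-individual level".
- **Use.** Section 2.2 wants to know whether a change in a biomarker exceeds random fluctuation. Section 1.13 allows biomarkers with too much variability to be dropped. Section 14.3 gives the variability results to the Delphi participants.

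Nothing in the Protocol postpones the Epley to the last repeat, takes Dix-Hallpike out of the repeats, or separates results obtained after an Epley.

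**The concern.** A test-retest study assumes that the condition measured is left alone between measurements, apart from natural variation. Here a positive result triggers a treatment aimed at the condition being measured, and the test is repeated within days. If the treatment works, the result goes from positive to negative because of what the study did. Section 14.1 has no separate place for such a change, so it falls into the within-individual component.

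The error has one direction: Dix-Hallpike looks less reproducible than it is. The results feed a possible decision to drop a biomarker and a Delphi panel. Without a flag, that panel could not tell a response to treatment from a poor test.

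**Working it through.** **The plan's own figure.** The example in 14.1 uses SDs of 0.5 (analytical), 1.0 (within) and 2.3 (between). ICC = 2.3² / (2.3² + 1.0² + 0.5²) = 5.29 / 6.54 = 0.81, against a stated value of about 80%. Simulating 20 participants at four visits gives 95% limits of about 0.64 to 0.89, against the stated 65% to 89%. The example is sound, but it concerns a continuous measure that nobody treats between visits.

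**What is not given.** Day-21 BPPV frequency, natural remission over 12 days, Epley success, accuracy of the test and the amount of usual care are all absent. The 40% in 1.5.1 comes from an acute TBI series. Every input below except that 40% is therefore an assumption, and the 40% itself may not apply at day 21. The 0/1 ICC is only an illustration, since 14.1 does not fix that statistic for a binary result.

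**Hand calculation, simplest case.** Assume 40% positive at the first visit, a perfect test, no remission, and Epley success of 50% per manoeuvre.

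| Result at the four visits | Probability given positive at first | Person mean | Within-person sum of squares |
|---|---|---|---|
| 1,0,0,0 | 0.500 | 0.25 | 0.75 |
| 1,1,0,0 | 0.250 | 0.50 | 1.00 |
| 1,1,1,0 | 0.125 | 0.75 | 0.75 |
| 1,1,1,1 | 0.125 | 1.00 | 0 |

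- Within mean square = 0.4 × (0.375 + 0.250 + 0.094) / 3 = 0.4 × 0.719 / 3 = 0.096, an SD of 0.31.
- Mean of the person means among positives = 0.469; mean of their squares = 0.289.
- Variance of person means = 0.4 × 0.289 − (0.4 × 0.469)² = 0.116 − 0.035 = 0.080.
- Between component = 0.080 − 0.096 / 4 = 0.057 (from unrounded values).
- ICC = 0.057 / (0.057 + 0.096) = 0.37. Without the Epley it would be 1.00, because no result would change.

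**Adding natural remission.** Let r be remission over 12 days and e the Epley success after each of visits 1 to 3 (perfect test). The chance that a first-visit positive has cleared by visit 4 is r without the Epley and 1 − (1 − r)(1 − e)³ with it. The share added by the Epley is the difference divided by the second figure. For r = 0.5 and e = 0.5: 1 − 0.5 × 0.125 = 0.9375, and (0.9375 − 0.5) / 0.9375 = 47%.

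| | r = 0 | r = 0.25 | r = 0.5 | r = 0.75 |
|---|---|---|---|---|
| e = 0.2 | 100% | 59% | 33% | 14% |
| e = 0.5 | 100% | 72% | 47% | 23% |
| e = 0.8 | 100% | 75% | 50% | 25% |

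**Adding test error.** Simulated mean ICC for 20 patients at four visits, with 2, 4 or 8 having BPPV at the first; repeat runs agree within about 0.01.

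| Assumed sensitivity, specificity, r | No Epley | e = 0.2 | e = 0.5 |
|---|---|---|---|
| Perfect test, 0.5 | 0.73–0.76 | 0.53–0.56 | 0.23–0.27 |
| 0.9, 0.98, 0.5 | 0.51–0.59 | 0.36–0.42 | 0.18–0.21 |
| 0.8, 0.95, 0.75 | 0.21–0.30 | 0.15–0.21 | 0.07–0.09 |

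The ICC falls in every row. The fall is nil if no patient has BPPV or the Epley never works.

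**The case against.** **Usual care.** Section 7.12 has results of known clinical utility passed promptly to treating clinicians, and 7.13 lets routine care continue without prohibited interventions. A patient with BPPV might be treated within the 12 days anyway. This stands as a limit on size: the shares above compare the Epley with natural remission alone and are upper figures for each scenario. If usual care cleared 20% of detected positives in each interval (4 positives, sensitivity 0.9, specificity 0.98, r = 0.5), the ICC with no study Epley would fall from about 0.58 to 0.42. The mechanism is untouched, since a response to treatment is not random fluctuation whoever delivers it.

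**Section 14.1 may not mean Dix-Hallpike.** Its tools suit continuous measures, and its reference to each Appendix 1 biomarker cannot be literal, because 1.13 leaves out the headache, mental health and cognition workstreams. That is fair about the form of the estimate. But 1.13 keeps the vestibular workstream in, and 7.6.2 repeats its tests, so the Protocol as written does cover Dix-Hallpike.

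**This is for the SOPs or the SAP.** Test order in an SOP cannot help, because Dix-Hallpike always precedes the Epley it triggers, and an SOP withholding the Epley would contradict 8.4. Recording the Epley may already be in SOPs or CRFs that are not shown. The conflict between the treatment rule and the analysis, however, is fixed in the Protocol itself.

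**Little depends on it.** No numerical threshold removes a biomarker: 1.13 only permits dropping, and the Delphi participants judge prognostic capability. In the 75% remission row the ICC is low even without an Epley. This is a good reason to grade the point as minor.

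**Stronger readings.** A reader might infer that vHIT gain, sway, walking or eye-movement measures are distorted too. The documents show no such effect. Nor do they support reading the 8.4 rule as wrong, since treating BPPV is reasonable care.

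**Conclusion.** The point holds in a limited form. Following the Protocol as written, a Dix-Hallpike positive cleared by the study's own Epley counts as within-person variability in the 20 mTBI patients of the clinical variability cohort. This conflicts with the purpose in 2.2 of separating real change from fluctuation.

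The direction is firm wherever at least one patient has BPPV and the Epley has some effect. The size is not known. Across the assumptions shown, the drop in ICC runs from small to large, and concurrent usual care would reduce the part due to the study. The consequence is confined to one non-primary biomarker. It does not follow that Dix-Hallpike would be dropped, only that the evidence given to those who decide would mislead on this item. The point is a minor, cheap improvement.

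**What to change.** 1. Leave the clinical rule in 8.4 as it is.
2. In the variability cohort, record each Epley with its visit, if the SOPs or CRFs do not already do so.
3. In 14.1, state that mTBI Dix-Hallpike results obtained after an Epley are post-treatment, that they are reported with the number of treated positives, and that they are not used as evidence of excess variability under 1.13 or in the Delphi process of 14.3.

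Two apparent repairs would not work. Leaving out treated patients removes every detected positive, so only negative results remain. A model term for visits after an Epley cannot separate its effect from natural remission, because every detected case is treated. A sensitivity analysis of the other vestibular measures without treated patients is optional and not needed for this point.

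The cost is one CRF field and a short addition to 14.1, with no extra visits and no change to care. The real price is accepting that, in effect, the study gives no usable test-retest estimate for Dix-Hallpike in mTBI patients with BPPV.
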